SLE is a chronic inflammatory disease that has renal effect in about half of patients. Lupus nephritis is a major risk factor for morbidity and mortality in patients with SLE, and in spite of strong anti-inflammatory and immunosuppressive therapies still ends in CKD or ESRD. (5)

Based on this observation, we aim to determine the effect of SGLT2i treatment in patients with glomerulonephritis secondary to SLE who either is diabetic or non-diabetic.

Aim of the work

This study aims to assess SGT2i role in regression of ongoing kidney and cardiac diseases among lupus nephritis patient either diabetic or non-diabetic under different immunosuppressive therapy.

Patients and methods

Technical design:

Study sitting: .1

Nephrology and renal transplant unit at urology and nephrology center in Mansoura University.

It will include 100 patients with lupus nephritis, Diagnosis of glomerulonephritis was performed by renal biopsy, and all of the renal biopsies were carried out at urology and nephrology center.

Patients with an estimated glomerular filtration rate (eGFR) >30 ml/min/1.73m2 will be randomized into two groups

- Study group will receive SGLT2i inhibitor as add on drug or replace
 another drug according to patient clinical situation, Dapagliflozin 10
 mg and 25 mg will be used once daily with or without food.
 - Control group will be maintained on placebo. •

The primary endpoint will be sustained decline in eGFR ≥50%, ESKD, or kidney or cardiovascular death

We will follow up all patients for 12 months and compare their results.

2. Inclusion criteria:

- Patients aged more than 16 year. .1
- Willing to sign informed consent. .2
- Diagnosis of SLE according to EULAR/ACR classification .3 criteria.
 - Renal biopsy showed lupus nephritis. .4
- Patient with eGFR > 30 ml/min/1.73m2 by cockcroft-gault .5 equation.

3. Exclusion criteria:

- Patients with eGFR <30 ml/min per 1.73 m2. .1
 - Current pregnancy or lactation. .2
- Medical history of chronic disease (CLD, cancer, severe .3 respiratory distress, gastrointestinal tract lesions).
- Patients refusing to participate in the study or lost follow up. .4
- Evidence of urinary obstruction of difficulty in voiding at .5 screening.

- Patients who are receiving high dose diuretics or combined .6 ACEI, ARBS.
- Patients who have frequent hypotensive episode or SBP .7 <100 mmHg.

Operational design:

Study Protocol:

Patients included in the study will treated with dapaglifilozin

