 initiated at a total daily dosage of 10 mg/kg per day.

Study design:

Type of the study: randomized controlled study.

The following data will be gathered and evaluated for all patients:

I-before intervention:

- Serum creatinine, Creatinine clearance. .1
- 24 hour urine protein, urine protein/creatinine ratio. .2
 - Urine analysis. .3
 - HBA1c. .4
 - HGB. .5
 - Uric acid and lipid profile. .6
 - Lupus serology. .7

II-after intervention: All patients will be evaluated monthly regarding:

- Serum creatinine, creatinine clearance. .1
- 24 hour proteinuria, protein/creatinine ratio. .2
- Fasting, random and postprandial glucose levels. .3
 - CNI trough level if used. .4
 - Urine analysis. .5
 - HGB level. .6
 - Uric acid, lipid profile. .7
 - Lupus serology. .8

Cardiovascular assessment: .9

ECCHO.

Atherosclerosis and vascular calcification incidence (NCCT model).

Regular measurement of blood pressure each visit.

Outcomes:

- Effect of dapagliflozin compared to placebo on eGFR. .1
- Effect of dapagliflozin compared to placebo on systolic/diastolic blood .2 pressure.
 - Effect of dapagliflozin compared to placebo on body weight. .3
- Safety of dapagliflozin vs. placebo the number of hypoglycemia .4 episodes between groups and serious adverse events.

Statistical Analysis:

Qualitative data were displayed in cross tabulations, and quantitative data were described in terms of arithmetic mean ± SD. Bivariate techniques were used for initial evaluation of contrasts. Thus, the chi-square and Fisher's exact tests were used for comparisons of frequencies of qualitative variables; the Mann-Whitney test and the unpaired t-test were used for comparisons of means of two quantitative variables. A p-value <0.05 was considered significant. Graft and patient survival rates were assessed using the Kaplan-Meier method. All analyses were carried out using the computer package SPSS for windows, release 16 SPSS Inc. Chicago, III, USA.

Administrative design •

Informed consent will be obtained from all subjects and the approval will be obtained from institutional review board (IRB) in Faculty of Medicine, Mansoura University. There is no funding.

Research question

The main research question is: Does use of SGLT2i will show superiority over conventional lines of treatment of lupus nephritis patient as regard efficacy and safety.

Rationale and justification

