The rational of this study is that SGLT2i are now one of the common lines in regression of chronic kidney disease either is diabetic or not.

Large trials on this issue exclude patient with glomerulonephritis, so we will study its renal efficacy in patient with secondary glomerulonephritis to SLE to prove their efficacy and safety in this group of patients.

Objectives

The main objective of this study is to:

- To compare use of SGLT2i versus standard care in regression of chronic kidney disease in patient with LN.
 - To study the safety and efficacy of this drug group with use of immunosuppression and possible interaction.

Hypothesis

leading causes SLE is the one of the of secondary glomerulonephritis. Despite the use immunosuppressive and antiproteinuric drugs, a number of patients are at risk of progressing to end-stage kidney disease. Additional therapies to slow kidney function decline are highly desired. The DAPA-CKD trial demonstrated that the sodium glucose co-transporter 2 inhibitor dapagliflozin significantly reduced the risk of kidney failure and prolonged survival in participants with chronic kidney disease with and without type 2 diabetes. The DAPA-CKD population excluded patients with lupus nephritis, so we determined the long-term efficacy and safety of dapagliflozin on major

kidney and cardiovascular outcomes in these patients.

References

- James Matera, DO. SGLT2 Inhibitors and CKD in -1 2021. Consultant360. Published online May 25, 2021.
- Dan Xu, Owain Chandler, Cleo Wee, et al. Sodium--2
 Glucose Cotransporter-2 Inhibitor (SGLT2i) as a Primary
 Preventative Agent in the Healthy Individual: A Need of
 August 2021
- Hiddo J.L. Heerspink, Ph.D., Bergur V. Stefánsson, et-3al. Dapagliflozin in Patients with Chronic Kidney Disease.N Engl J Med 2020; 383:1436-1446.
- Kana N. Miyataa, Shao-Ling Zhanga John S.D. Chana-4. The Rationale and Evidence for SGLT2 Inhibitors as a-4Treatment for Nondiabetic Glomerular Disease.CJASN May 2017, 12 (5) 825-835.
- Salem Almaani, Alexa Meara and Brad H. -5 Rovin. Update on Lupus Nephritis Clin PharmacolTher 2007;81:228-34. 10.1038/sj.clpt.6100039.

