Statistical Analysis Plan

Document Control

Title: Statistical Analysis Plan for the Study of SGLT2 Inhibitors in Lupus Nephritis Patients

Protocol ID: [NCT05748925] Version: 1.0 Date: [11/3/2024] Principal Investigator: [[name]] Statistician: [[name]] Approval Signatures: Principal Investigator: [name] Statistician: [name]

Table of Contents

- 1. Introduction
- 2. Study Design
- 3. Study Objectives
- 4. Endpoints
- 5. Sample Size Justification
- 6. Statistical Methods
- 7. Handling of Missing Data
- 8. Interim Analysis
- 9. Safety Analysis
- 10. Data Quality and Management
- 11. Software
- 12. Appendices

1. Introduction

• **Purpose of the SAP**: This document outlines the statistical approach for analyzing data from the clinical trial studying the effects of SGLT2 inhibitors on renal, cardiovascular, and hematological outcomes in lupus nephritis patients.

2. Study Design

Design: Randomized, double-blind, placebo-controlled clinical trial.

Study Duration: Conducted from September 2022 to November 2023

Randomization: Patients were randomly assigned to either dapagliflozin (10 mg once daily) or placebo groups using computer-generated random tables in a 1:1 ratio stratified by age and gender.

Blinding: The study was double-blinded, and all trial staff and participants remained unaware of individual treatment assignments until study completion.

3. Study Objectives

Primary Objective: To evaluate the impact of SGLT2 inhibitors on renal, cardiovascular, and hematological parameters in lupus nephritis patients.

Secondary Objective: To explore changes in body weight, BMI, and other echocardiographic and iron profile parameters over 12 months.

4. Endpoints

Primary Endpoints

Renal Function: Serum creatinine, eGFR, and 24-hour urine protein

Cardiovascular Health: BNP levels and coronary calcification via NCCT

Hematological Parameters: Hemoglobin and erythropoietin levels

Hepcidin Level: Measured before and after intervention

Secondary Endpoints

Body Weight and BMI: Assessed at baseline and follow-up visits.

Echocardiographic Findings: Assessed pre- and post-intervention.

Iron Profile: Serum ferritin and TSAT

5. Sample Size Justification

Calculation: A sample size of 100 patients was targeted, accounting for potential dropouts, to provide sufficient power (80%) at a significance level of 0.05 to detect differences between the two groups.

6. Statistical Methods

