
General Considerations

Significance Level: A two-sided alpha level of 0.05 will be used for all primary analyses.

Analysis Populations:

Intent-to-Treat (ITT): All randomized patients will be analyzed according to their assigned group.

Per-Protocol (PP): Only patients completing the study without major protocol violations.

Primary Endpoint Analysis

Renal Outcomes: ANOVA for repeated measures for serum creatinine and eGFR if normally distributed, and the Friedman test for non-normally distributed data. Post-hoc tests using Bonferroni correction.

Cardiovascular Outcomes: Mann-Whitney U test for BNP levels and coronary calcification between groups.

Hematological Outcomes: Paired t-test for hemoglobin and erythropoietin levels if data is normally distributed; otherwise, Wilcoxon signed-rank test.

Secondary Endpoint Analysis

Body Weight and BMI: Compared over time using ANOVA for repeated measures.

Echocardiographic Parameters: Analyzed with paired t-tests, adjusted with Bonferroni correction.

Iron Profile: Analyzed pre- and post-intervention using ANOVA or Kruskal-Wallis for non-normally distributed variables.

Categorical Variables

Chi-Square Test: For between-group comparisons of categorical data (e.g., presence of diabetes, hypertension).

7. Handling of Missing Data

Imputation: Last observation carried forward (LOCF) for data missing at random; multiple imputation for extensive missing data.

Sensitivity Analysis: Conducted to evaluate the robustness of primary endpoint findings against different missing data assumptions.

8. Interim Analysis

Timing: An interim analysis is planned at the halfway point (6 months).

Stopping Rules: An O'Brien-Fleming approach will be applied to adjust the significance threshold for interim testing, allowing for an earlier stop for efficacy or safety concerns.

9. Safety Analysis

Adverse Events (AEs): Summarized by type, frequency, and severity. Fisher's exact test will be used to compare AE rates between groups.

Specific Safety Parameters: Monitoring for hypotension, electrolyte imbalances, and kidney function.

10. Data Quality and Management

Data Quality Measures: Includes data verification, regular audits, and query resolution.

Database Lock: Data will be locked and verified prior to the final analysis.

11. Software

Statistical Software: All analyses will be conducted using SPSS (Version 25).

12. Appendices

	Control group. (n= 41)	Study group. (n= 38)	P value

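### A SAP dated after trial end drops the protocol's composite primary endpoint without a reason and names eight primary variables, with no rule for what makes the trial positive

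*SAP*

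**What the plan says.** **Protocol.** Patients and methods gives a single primary endpoint: "The primary endpoint will be sustained decline in eGFR ≥50%, ESKD, or kidney or cardiovascular death". The Hypothesis section likewise speaks of major "kidney and cardiovascular outcomes in these patients". The separate Outcomes list omits the composite. It is not labelled primary; its first item is "Effect of dapagliflozin compared to placebo on eGFR", followed by blood pressure, body weight and safety. For quantitative variables, Statistical Analysis names comparisons between groups: "the Mann-Whitney test and the unpaired t-test were used for comparisons of means of two quantitative variables". It also names a time-to-event method: "Graft and patient survival rates were assessed using the Kaplan-Meier method".

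**SAP.** Document Control reads "Version: 1.0 Date: [11/3/2024", and section 2 reads "Study Duration: Conducted from September 2022 to November 2023". By section 2, blinding lasted only until the study was complete. Section 4 lists eight primary variables: serum creatinine, eGFR, 24-hour urine protein, BNP, coronary calcification, haemoglobin, erythropoietin and hepcidin. The composite appears neither there nor in section 6. On error control, section 6 says "A two-sided alpha level of 0.05 will be used for all primary analyses". Bonferroni is named only for post-hoc tests under renal outcomes and for echocardiography. Section 8 plans a 6-month O'Brien-Fleming look that is tied to no endpoint. Section 5 claims 80% power for 100 patients without naming an endpoint or effect size. The appendix tabulates results for 41 control and 38 study patients.

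**The concern.** There are three linked problems.

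- **The protocol's question is dropped.** A reader of the final analysis would not learn whether the drug affected the endpoint that the trial was set up to test, or that it had been replaced.
- **No success rule.** With eight primary variables at 0.05 each, the plan does not say whether one success, all eight or some ordering counts. The choice is left to whoever reads results that already exist.
- **Tests that do not compare arms hold primary position.** Section 6 gives haemoglobin and erythropoietin paired tests and names no test for hepcidin or 24-hour protein. It gives creatinine and eGFR a repeated-measures ANOVA, which the Table 6 footnote reports as within-group. Only BNP and calcification have an explicit between-group test. A change within the treated arm can reach significance when the control arm changes just as much.

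**Working it through.** **1. Timing.** From 30 November 2023 to 11 March 2024 is 102 days; to 3 November 2024 it is 339 days. Both readings of the date fall after trial end.

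**2. Count and origin of the variables.** 3 renal + 2 cardiovascular + 2 haematological + hepcidin = 8. In the protocol, eGFR is a listed outcome. Creatinine, 24-hour protein, haemoglobin and calcification by NCCT are scheduled measurements. BNP, erythropoietin and hepcidin do not appear in the protocol text provided.

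**3. Within-arm against between-arm results (SAP Tables 6 to 8).**

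| Variable | Within-arm P, control / study | Between-arm P at 12 months, printed | Recomputed |
|---|---|---|---|
| Creatinine | 0.1 / 0.01 | 0.8 | medians only |
| eGFR | 0.003 / 0.001 | 0.9 | 0.14 |
| 24-hour protein | 0.06 / 0.07 | 0.6 | medians only |
| Haemoglobin | 0.08 / 0.06 | 0.6 | 0.65 |
| Erythropoietin | 0.08 / 0.1 | 0.6 | 0.61 |
| Hepcidin | 0.001 / 0.001 | 0.2 | 0.26 |

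The recomputed values are pooled t tests from the 12-month means and SDs at 41/38. For eGFR, the pooled SD is √[(40×44.5² + 37×48²)/77] = 46.2 and the standard error is 46.2×√(1/41 + 1/38) = 10.4. Then t = (115.7 − 100.3)/10.4 = 1.48 and P = 0.14. The printed 0.9 conflicts with the table's own means and SDs.

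Three of the six reach P<0.05 within the study arm; none does between arms. Study-arm eGFR fell and median creatinine went from 0.8 to 0.9, so of the three only hepcidin could be read as a benefit. Mean changes, control v study:
- hepcidin: 128 − 198 = −70 v 116 − 182 = −66 ug/L
- eGFR: 100.3 − 114 = −13.7 v 115.7 − 128 = −12.3

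**4. Calcification (Tables 5 and 9).** Pearson chi-square gives P = 0.012 at baseline (3/41 v 11/38) and P = 0.001 at 12 months (1/41 v 11/38). Both agree with the printed values. The study-arm count did not change.

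**5. Family-wise error (illustration).** If any one of eight valid between-arm tests at 0.05 counted as success, independence gives 1 − 0.95⁸ = 0.337. Simulated tests with an assumed common correlation of 0.5 or 0.8 give 0.25 or 0.16. For the two variables with an explicit between-group test, independence gives 1 − 0.95² = 0.0975.

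**6. What the composite could show.** Events needed for 80% power at two-sided 0.05 with 1:1 allocation are 4(1.96 + 0.84)²/(ln HR)². The hazard ratios are assumptions, since the documents give none.

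| Assumed HR | Events |
|---|---|
| 0.4 | 37 |
| 0.5 | 65 |
| 0.6 | 120 |
| 0.7 | 247 |

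Sixty-five events would be 65/79, about 83% of the tabulated patients, or 65% of the 100 targeted. At 0.6 or 0.7 the requirement exceeds the number of patients.

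**7. Section 5's power claim.** It cannot be reproduced without an endpoint or effect size. Solving backwards (noncentral t, 80% power), the detectable standardized difference is:

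| Level | 50/50 | 41/38 |
|---|---|---|
| 0.05, one unadjusted test | 0.57 | 0.64 |
| 0.05/8 = 0.00625, first Holm step | 0.73 | 0.83 |

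**The case against.** **The variables are not all new.** This stands. Five of the eight are a listed outcome or scheduled measurements in the protocol. A reader might infer that the eight were picked after the results were seen. The documents do not support that: the date and the appendix show when this version was written, not when the choice was made. They support only the statement that primary status first appears in a post-trial document.

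**Between-arm P values are printed.** Tables 6 to 8 give them for all six variables, and the footnotes name tests, including for hepcidin. This also stands, but section 6 does not make those comparisons primary, and it is section 6 that decides what may be claimed. That a within-arm result would in fact be headlined is a risk, not something the documents show.

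**The 34% is hypothetical.** Correct. A reader might take it as the trial's actual error rate, but the SAP states no any-one-success rule and several of its tests do not compare arms.

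**The calcification result might be read as harm.** The tables do not support this either. The arms already differed at baseline and the study arm stayed at 11/38. Controlling alpha would not remove that imbalance.

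**The composite is underpowered.** True, but this is a reason to say so, not to drop a protocol primary endpoint without comment.

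**Bonferroni and O'Brien-Fleming are in the SAP.** Neither covers multiplicity across the eight primary variables.

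**Conclusion.** The point holds, and the SAP should not stand as written. It makes an undeclared change of primary endpoint, in a document dated 102 or 339 days after trial end and carrying results by arm, with no success rule. These facts rest on the documents alone. The consequence is visible in the SAP's own tables: three of six variables are significant within the study arm and none between arms at 12 months. Of the other two, BNP is printed at 0.9 between arms, and calcification largely reflects baseline imbalance.

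The 34%, 25% and 16% error rates and the 37 to 247 events depend on the stated assumptions. The recomputed P values assume that 41 and 38 patients contribute at 12 months.

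**What to change.** 1. **SAP 4 and 6, primary endpoint.**
   - Restore the protocol composite as the single primary endpoint, derived from recorded visits with one stated eGFR equation. Declare the endpoint change and its date.
   - Report event counts by component and arm, with Kaplan-Meier and log-rank as far as the data allow.
   - The protocol does not define how a decline is confirmed as sustained. Label whatever operational definition is used as post hoc, and add a sensitivity count of unconfirmed declines.
   - State whether the 6-month O'Brien-Fleming look took place and on which endpoint. Use 0.05 for the final test only if no alpha was spent; otherwise use the remaining O'Brien-Fleming level.
   - State that the composite is likely to be inconclusive, giving the event requirement with its hazard ratio labelled as an assumption.
2. **SAP 4 and 6, the eight variables.**
   - Relabel them as secondary. Note that their primary status first appeared in a SAP dated after trial end, and that BNP, erythropoietin and hepcidin are not in the protocol text provided.
   - In place of within-arm tests, compare each between arms at 12 months, adjusted for its own baseline, with Holm across the eight. State that no single success makes the trial positive.
   - Only 3 controls had calcification at baseline, so that adjusted comparison will be imprecise.
   - Recompute the tabulated between-arm P values, starting with 12-month eGFR (printed 0.9, recomputed 0.14).
3. **SAP 5.** Replace the unqualified 80% with figures that match the analyses: the event requirement for the composite, and a detectable standardized difference of 0.73 (50/50) or 0.83 (41/38) at the first Holm step. If 0.57 or 0.64 is given, label it as applying only to a single unadjusted test at 0.05.

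**Cost.** SAP wording and re-analysis of data already recorded; no new patients. The price is stricter thresholds, a less favourable power statement and a probably inconclusive primary result. None of this restores prespecification; it makes the change visible.

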Cholesterol mg/dL mean ± SD	185 ± 46	172 ± 40.7	0.5
Albumin (g/dL) mean ± SD	3.7 ± 0.4	3.7 ± 0.3	0.4
Random blood sugar (mg/dL) Median (min, max)	89 (66, 568)	92.5 (64, 243)	0.4
Uric acid (mg/dL) mean ± SD	6.2 ± 2.1	6.5 ± 1.7	0.2
Alanine aminotransferase (IU/L) Median (min, max)	17 (2, 84)	17 (7, 82)	0.8
Aspartate aminotransferase (IU/L) Median (min, max)	21(9, 66)	19 (12,72)	0.4
Sodium (mEq/L) mean ± SD	137 ± 3.1	136 ± 3	0.5
Potassium (mEq/L) mean ± SD	3.9 ± 0.4	4 ± 0.4	0.3

eGFR: estimated glomerular filtration rate; (Student T test or Mann-Whitney) for continuous data, and chisquare test for categorical data. Continuous data are expressed as mean (SD) or median (minimum – maximum). Categorical data are expressed as number (percentage). Level of significance < 0.05.

Table (4): Baseline hematological findings:

	Control group. (n= 41)	Study group. (n= 38)	P value		
Hemoglobin (g/dL) Mean \pm SD	11.9 ± 1.9	11.7 ± 1.7	0.5		
MCV (FL) Mean ± SD	82 ± 7	84 ± 6.9	0.9		
MCH (Pg) Mean ± SD	25.4 ± 2.9	26.3 ± 2.9	0.9		
Ferritin (mg/dL) Median (min, max)	60 (13, 1113)	33.5 (3, 1460)	0.09		
TSAT (%) Median (min, max)	23.8 (7, 64)	18 (6, 74)	0.05		
Erythropoietin level (IU/L) Mean ± SD	11.6 ± 2.1	11.3 ± 1.4	0.1		
Hepcidinlevel(ug/L) $Mean \pm SD$	198 ± 74	182 ± 76	0.3		
Platelet count (*10 ³) Mean \pm SD	288 ± 71	300 ± 79	0.7		

McW Mean corpuscle volume; MCH: Mean corpuscular hemoglobin; TSAT: Transferrin saturation test; (Student T test or Mann-Whitney) for continuous data, and chi-square test for categorical data. Continuous data are expressed as mean (SD) or median (minimum – maximum). Categorical data are expressed as number (percentage).; Level of significance < 0.05.

Table (5): Baseline Cardiac evaluation:

Control group. Study group. P value

	(n= 41)	(n= 38)	
Coronary calcification No. (%)	3 (7.3%)	11 (28.9%)	0.012
Coronary calcification severity No. (%) - No - Minimal - Mild - moderate	38 (92.7%) 1 (2.4%) 1 (2.4%) 1 (2.4%)	27 (71.1%) 3 (7.9%) 7 (18.4%) 1 (2.6%)	0.04
BNP (ng/L) Median (min, max)	52 (40, 557)	52 (34, 90)	0.8
Echocardiographic	c finding		0.6
EF % Mean \pm SD	65.4 ± 9.3	64.6 ± 5.4	0.6
LAD (ml) Mean ± SD	24.2 ± 7.6	24.9 ± 7.6	0.6
Aortic diameter (ml) Mean ± SD	24.7±7.4	24.8±7.1	0.9
ESV (ml/m) Median (min, max)	38±13.6	41±13.9	0.4
EDV (ml/m) Mean ± SD	98±35.7	111.5±31.6	0.08

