BNP: Brain natriuretic peptide; EF: Ejection fraction; LAD: Left atrial dimension; ESV: End-systolic volume; EDV: End diastolic volume; (Student T test or Mann-Whitney) for continuous data, and chi-square test for categorical data. Continuous data are expressed as mean (SD) or median (minimum – maximum). Categorical data are expressed as number (percentage).; Level of significance < 0.05.

Table (6): Comparison between study and control groups as regard effect of intervention on
 disease activity and renal affection at different time points

	Grouping	Baseline	3 months	6 months	9 months	12 months	P value*
Consumed C3 & C4	Control	5 (12.2%)	5 (12.2%)	4 (9.8%)	6 (14.6%)	10 (24.4%)	0.1
No. (%)	Study	2 (5.3%)	5 (13.2%)	2 (5.3%)	6 (15.8%)	6 (15.8%)	0.1
	P value**	0.4	0.9	0.3	1	0.4	
S. creatinine (mg/dL)	Control	0.8 (0.4, 2.7)	0.9 (0.4, 3.1)	0.9 (0.3- 3.1)	0.9 (0.6, 4)	0.9 (0.6, 5)	0.1
Median (min, max)	Study	0.8 (0.4, 2.6)	0.9 (0.6, 2.6)	0.9 (0.5, 3.1)	1 (0.5, 4.2) a	0.9 (0.5, 5)	0.01
	P value**	0.8	0.8	1	0.5	0.8	
eGFR (ml/min/m²) Mean ± SD	Control	114±51	104±45 a	107±53.8	99±47 a	100.3±44.5 a	0.003
	Study	128±59.7	115±47 A	118±50 A	109±44.5 a, c	115.7±48 a	0.001
	P value**	0.6	0.9	0.8	0.2	0.9	
	Control	0.4(0.06- 3.6)	0.6 (0.03-5)	0.6 (0.03- 7)	0.6 (0.02, 5)	0.5 (0.02 , 8)	0.06
24- hour urinary protein (g/24 hours) Median (min, max)	Study	0.6 (0.07-3)	0.7 (0.01-4)	0.8 (0.02, 4.8)	0.6 (0.05, 4.7)	0.5 (0.02 , 4)	0.07
	P value**	0.3	0.9	0.8	0.6	0.6	
Albumin (g/dL)	Control	3.7±0.4	3.7±0.4	3.6±0.4	3.8±0.4 c	3.9±0.3 a, b, c	0.001
iviean ± SD.	Study	3.7±0.3	3.7±0.5	3.7±0.3	3.8±0.3 c	3.9±0.8 a, c	0.04
	P value**	0.4	0.9	0.1	0.7	0.8	

(*) Within group analysis (repeated measure ANOVA).

(**) Between group analysis (Student T test or Mann-Whitney) for continuous data, and chi-square test for categorical data. Post-hoc analysis;

(a) significance against baseline <0.05; (b) significance against 3 months level <0.05, (c) significance against 6 months level <0.05, (d)

significance against 9 months level <0.05. Continuous data are expressed as mean (SD) or median (minimum – maximum). Categorical data are expressed as number (percentage).

Table (7): effect of intervention on hematological findings between both groups at different time points:

	Grouping	Baseline	3 months	6 months	9 months	12 months	P value*
Haemoglobin (g/dL) Mean ± SD	Control	11.9±1.9	12.2±1.9	11.8±2.5	12±1.9	12.2±1.9	0.08
	Study	11.8±1.8	12.3±1.7	12±2.5	11.9±2.2	12±2	0.06

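### SAP 6 gives the primary endpoint hepcidin no test and does not name 24-hour urine protein, and the Table 6 footnote departs from SAP 6's own rule for skewed renal data

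*SAP*

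**What the plan says.** SAP 4 lists as primary "Renal Function: Serum creatinine, eGFR, and 24-hour urine protein" and, under its own label, "Hepcidin Level: Measured before and after intervention".

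For the renal group, SAP 6 prescribes "Renal Outcomes: ANOVA for repeated measures for serum creatinine and eGFR if normally distributed, and the Friedman test for non-normally distributed data". Its haematological line names haemoglobin and erythropoietin only, so hepcidin appears nowhere in SAP 6. For BNP, SAP 6 names a Mann-Whitney test between groups. The general rule is "A two-sided alpha level of 0.05 will be used for all primary analyses".

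SAP 12 already holds results up to 12 months:

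- **Table 6** carries one within-group footnote for all its rows, "Within group analysis (repeated measure ANOVA)". Its between-group footnote allows either a t-test or Mann-Whitney for continuous data, and chi-square for categorical data.
- **Table 8** tests hepcidin within each arm by paired t-test.
- **Table 5** labels baseline BNP "BNP (ng/L) Median (min, max)", while Table 9 gives BNP at 12 months as mean ± SD.

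**The concern.** A primary endpoint needs one identifiable test of drug against placebo, fixed in advance. Hepcidin has none. Urine protein has one only if the reader takes the Friedman clause to cover it, and that test has no group term.

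The renal rule also depends on the data, since the method follows from a look at the distribution. Table 6 then shows a method that the rule would not have chosen for its skewed rows. A reader cannot tell which test produced the study-arm creatinine p-value of 0.01, or the within-arm protein p-values of 0.06 (control) and 0.07 (study). The protein values lie close enough to 0.05 for the choice of test to matter.

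An analysis of untransformed grams per day would be dominated by a few heavily proteinuric patients, at a cost in power.

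**Working it through.** **1. The plan's own figure.** SAP 5 sets a target of 100 with an unquantified allowance for dropout. The stated aim is "to provide sufficient power (80%) at a significance level of 0.05 to detect differences between the two groups". It names no endpoint, effect, SD or dropout rate, so 100 cannot be reproduced. Inverted, 50 per arm detects (1.96 + 0.84) × √(2/50) = 0.56 SD. The tabulated 41 v 38 detects 2.80 × √(1/41 + 1/38) = 0.63 SD. The plan does not say on which scale that SD is measured.

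**2. Are the renal rows skewed?** Distance from median to maximum, divided by distance from minimum to median, using Table 6 at 12 months:

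| Row | Calculation | Ratio |
|---|---|---|
| Protein, control | (8 − 0.5)/(0.5 − 0.02) | 15.6 |
| Protein, study | (4 − 0.5)/(0.5 − 0.02) | 7.3 |
| Creatinine, control | (5 − 0.9)/(0.9 − 0.6) | 13.7 |
| Creatinine, study | (5 − 0.9)/(0.9 − 0.5) | 10.2 |

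Over all visits the ratio runs from 4.5 to 15.6 for protein and from 3.7 to 13.7 for creatinine. Neither is plausibly normal untransformed, so SAP 6's rule points to Friedman. The footnote shows ANOVA.

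**3. Spread on the log scale.** Log SD ≈ ln(max/min) divided by the expected normal range (4.34 SD for n = 41, 4.28 SD for n = 38).

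- Protein, baseline: ln(3.6/0.06)/4.34 = 0.94 (control); ln(3/0.07)/4.28 = 0.88 (study).
- Protein, 12 months: ln(8/0.02)/4.34 = 1.38 (control); ln(4/0.02)/4.28 = 1.24 (study).
- Creatinine, all visits: 0.34 to 0.54.

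**4. Between-arm power at 12 months.** Simulated lognormal data, 41 v 38, two-sided 0.05. The effect sizes are assumptions.

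| Setting | Raw t-test | Mann-Whitney | Log t-test |
|---|---|---|---|
| Protein, log SD 1.1, 40% lower | 34% | about 50% | 53% |
| Protein, log SD 1.1, 50% lower | 56% | about 77% | 79% |
| Creatinine, log SD 0.45, 20% lower | 53% | 56% | 58% |

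**5. Within-arm power.** n = 38, five visits, fall from month 3 onward, raw and log ANOVA with Greenhouse-Geisser correction. Falls and visit correlations are assumptions; paired entries are for correlation 0.5 / 0.8.

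| Setting | Raw ANOVA | Friedman | Log ANOVA |
|---|---|---|---|
| Protein, log SD 0.94, 30% fall | 34% / 69% | 54% / 91% | 62% / 97% |
| Protein, log SD 1.3, 30% fall | 8% / 20% | 28% / 66% | 32% / 75% |
| Creatinine, log SD 0.45, 20% fall, correlation 0.5 | 82% | 78% | 86% |

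**6. Why a within-arm test does not answer the question.** In Table 8, hepcidin fell by 198 − 128 = 70 in controls and by 182 − 116 = 66 in the study arm. The within-arm p-value is 0.001 in both. The falls differ by 4 µg/L, and the between-arm p-value at 12 months is 0.2.

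**7. BNP.** In a sample of n, no value can exceed the mean by more than SD × (n − 1)/√n. For controls at 12 months (66 ± 22.1) the largest possible value is 66 + 22.1 × 40/√41 = 204. The control maximum at baseline was 557. Table 9 prints no group size, but its 1 (2.4%) fits 41.

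**The case against.** Several stronger readings are tempting and do not stand.

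- **That urine protein has no method at all.** SAP 4 places it under renal function, and the Friedman clause under the renal heading can fairly be read to cover it. It is unnamed and ambiguous, not absent.
- **That the ANOVA was run on raw values.** The footnote states no scale, and a single generic note under a mixed table may be incomplete labelling.
- **That the treatment comparison of protein lost much of its power.** The between-group footnote allows Mann-Whitney, and the median (min, max) display suggests it. If it was used, the loss against the log scale is only about 2 to 3 points.
- **That the yes/no row breaches SAP 6.** Complement consumption is not a SAP endpoint, and SAP 6 sets no within-group method for binary data. ANOVA is unsuitable there, but it contradicts no rule.
- **That the primary p-values cannot be interpreted.** The footnote conflict touches the within-group column; the between-arm p-values have their own stated methods.

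Rank tests are valid here, so the log scale is preferred mainly because it gives an effect size with an interval and admits baseline adjustment.

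It could also be said that repeated-measures ANOVA in SAP 6 was meant to include a group factor. SAP 6 does not say so, Table 6 labels it within-group, and Friedman has no group factor.

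What survives is the gap for hepcidin, the unnamed protein test, the conflict between SAP 6 and Table 6, and the lack of one specified between-arm analysis for these endpoints.

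**Conclusion.** The point holds as a gap in specification and a conflict between SAP 6 and its own tables. That part rests on the text alone and needs no simulation.

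The size is conditional. For protein, a raw-scale between-arm t-test would cost about 19 points of power against the log scale in the 40% setting (34% v 53%); Mann-Whitney would cost about 3. Within an arm, raw ANOVA would cost about 20 to 46 points against Friedman for a 30% fall. For creatinine the loss is immaterial, and at correlation 0.5 raw ANOVA slightly beats Friedman. These figures assume lognormal data, log SDs read from printed ranges, and assumed effects and visit correlations. They are illustrations, not estimates of what happened in this trial.

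The BNP bound is arithmetic, given 41 controls. A reader might infer that an inconvenient value was removed, but the documents do not show that. Either that patient's BNP fell by at least 557 − 204 = 353, or the patient is not in the 12-month summary, or one of the printed figures is wrong. Source data must decide.

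**What to change.** In SAP 6:

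1. Replace the normality-dependent switch with one between-arm, baseline-adjusted analysis per primary endpoint.
2. For 24-hour protein, creatinine and BNP, use the log scale and report the drug/placebo ratio of geometric means with a 95% CI.
3. Give hepcidin a between-arm, baseline-adjusted comparison. Nothing in the tables shows skew that would require logs.

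In SAP 12:

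4. Correct the Table 6 footnote, and any p-values affected, to the test and scale actually used. Give the complement row a method suited to binary data.
5. Print BNP with the same summary at both times, and check the 557 against source.

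Label all of this as post-hoc correction, because the SAP already contains results.

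The cost is wording and a re-run on existing data. The small downside is that effects on protein are reported as ratios rather than in g/24 h.
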